Dietary patterns research has overcome the limitations of single nutrient research to a large extent but not completely. Methodological issues have hindered a wider translation of findings from dietary patterns research, the major critique being lack of consistency and scientific rigor in the methods. In Aim 1a we will utilize a standardized methodology to evaluate the associations of the 8 dietary patterns with all-cause mortality as a marker for overall health and with CRC risk, adjusting for the same set of potential confounders, and further investigate in Aim 1b several inflammatory markers (CRP, IL6, TNFR, and adiponectin) and hyperinsulinemia (C-peptide) as mediators of the association between dietary patterns and CRC risk. This will provide an unprecedented opportunity to evaluate the consistency of evidence for the benefits of diet quality for overall health and for CRC prevention, supported by strong epidemiological methods and biological plausibility.

Methodological Approach

Study Population: The NHS was established in 1976 as a prospective cohort of 121,701 U.S. registered female nurses who were aged 30 to 55 years at enrollment.^{61,62} The HPFS was initiated in 1986 as a prospective cohort of 51,529 U.S. male health professionals who were aged 40 to 75 years.⁶³ Blood samples were collected from subpopulations of the NHS (n=32,826) in 1989-1990 and HPFS (n=18,225) from 1993 to 1994, using similar protocols for all cohorts.^{64,65}

Assessment of dietary data: Dietary data are updated every four years in the NHS (since 1980), NHS-II (since 1991) and in the HPFS (since 1986) with a validated semi quantitative food frequency questionnaire (FFQ) assessing habitual intake of foods and beverages over the preceding year. Participants reported how often, on average, they consumed each food of a standard portion size.⁶⁶⁻⁶⁸ We will use average dietary data cumulatively across the multiple FFQs, to reduce within-subject variation and best represent long-term diet.^{69,70}

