Assessment of lifestyle factors: We will calculate cumulative body mass index (BMI), physical activity levels, and pack-years smoked.⁷¹ Correlation between technician-measured and self-reported weight was $r=0.96$ in 1980 and 0.97 in 1986 and did not differ by level of BMI.⁷² Our methods that measure physical activity and diet have been rigorously validated in our cohorts.⁷³⁻⁷⁶ We have also routinely collected information regarding a CRC family history in a first-degree relative, post-menopausal hormone therapy, and aspirin use.^{77,78} These long-term lifestyle data at multiple time points provide an unprecedented documentation of individual's lifestyle factors and will allow us to account for within-person variation in the effect of lifestyle on CRC risk.

Assessment of biomarkers: Procedures for the measurement of plasma inflammatory markers (IL6, CRP, TNFaR2, and adiponectin),^{64,79,80} and plasma insulinemic markers (C-peptide, TG, and HDL)^{80,81} have been described. The intra-assay coefficient of variation from blinded quality control (QC) samples ranged from 2.9% to 12.8% for IL6, 1.0% to 9.1% for CRP, 4.0% to 10.0% for TNFaR2, 8.1% to 11.1% for adiponectin, <12% for C-peptide and <1.8% for TG and HDL across batches. In the nested case-control studies in which these biomarkers were measured, samples from cases and their matched controls were analyzed in the same batch. QC samples were randomly interspersed among the case-control samples, and laboratory personnel were blinded to QC and case-control status for all assays. Our group has previously documented the stability of biomarkers in whole blood for 24 to 48 hours.⁸² Participants who provided blood samples were cancer free and similar to their overall cohort with respect to BMI, parity, age at menarche, and past oral contraceptive use.⁸⁰

Ascertainment of CRC incidence^{83,97,98} and mortality:^{80,81} Information on incident cancer and other disease

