
Preliminary study 1 - Development and validation of an empirical index of dietary inflammatory potential (EDII): The goal for developing the **EDII** was to empirically create a score based on food groups to assess the overall inflammatory potential of whole diets. We first calculated average daily intakes (per 1000kcal) of 39 previously

defined food groups⁷⁰ from the 1986 and 1990 FFQs in the NHS. We then applied reduced rank regression (RRR) to derive a dietary pattern predictive of three inflammatory biomarkers: CRP, TNFaR2 and IL6. RRR identifies linear functions of predictors (e.g., food groups) that simultaneously explain as much variation in the responses of interest (e.g., biomarkers) as possible. The first factor obtained by RRR was retained for subsequent analyses; (we called this the RRR dietary pattern). We then used stepwise linear regression analyses to identify the most important component food groups contributing to the RRR dietary pattern with the biomarker response score (RRR dietary pattern) as the dependent variable,

[figure not shown]
Table 2: Multivariable-adjusted relative concentrations (95% confidence intervals) of inflammatory markers across quintiles of the EDII in the NHS-II and HPFS							
Quintile 1	Quintile 3	Quintile 5	Ptrend ^a	Quintile 1	Quintile 3	Quintile 5	Ptrend ^a
Nurses' Health Study-II (n=1,002); 1995-1999				Health Professionals Follow-up Study (n=2,633); 1990-1994			
IL6 ^b							
reference	0.99 (0.86, 1.13)	1.13 (0.99, 1.30)	0.09	reference	1.04 (0.96, 1.16)	1.15 (1.05, 1.25)	<0.0001
CRP ^b							
reference	1.25 (0.97, 1.60)	1.41 (1.11, 1.84)	0.08	reference	1.23 (1.09, 1.39)	1.39 (1.21, 1.57)	<0.0001
TNF α R2 ^b							
reference	1.00 (1.01, 1.10)	1.07 (1.03, 1.12)	0.04	reference	1.05 (1.02, 1.09)	1.09 (1.06, 1.13)	<0.0001
Adiponectin ^b							
reference	1.01 (0.92, 1.10)	0.88 (0.81, 0.97)	0.008	reference	0.95 (0.90, 1.00)	0.87 (0.82, 0.92)	<0.0001
Overall inflammatory marker score ^{c,d}							
reference	1.45 (0.89, 2.37)	2.69 (1.64, 4.41)	0.002	reference	1.61 (1.26, 2.07)	2.64 (2.05, 3.39)	<0.0001

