Statistical Analysis: The primary analysis for **Aim 1a** will prospectively assess associations between each of the 8 dietary patterns and all-cause mortality, and with incident CRC, using Cox proportional hazards regression, with separate models for men and women and in pooled analyses. For CRC, we will investigate associations by anatomic subsite (proximal colon, distal colon, rectum). After >30 years of follow-up, we have confirmed 31,286 all-cause deaths in the NHS and 12,555 in the HPFS.⁹⁴ Also, we have identified 1,764 CRC cases (823 proximal, 521 distal, and 379 rectal cancers) in NHS, and in the HPFS, we documented 1,640 CRC cases (640 proximal, 574 distal, and 426 rectal cancers).⁹⁵⁻⁹⁷ Person-time (in months) for each participant will be calculated from the date of return of the baseline questionnaire in 1980 for women and 1986 for men, until the date of death from any cause or until CRC diagnosis, or June 1, 2012 whichever came first. Cumulatively updated average dietary pattern scores will be calculated using information from all available FFQs up to the 2-year interval prior to the follow-up cycle in which death or CRC diagnosis was confirmed. We will categorize the dietary patterns into quintiles and use the lowest quintile as reference, stratifying the Cox models on calendar year, age in months, to estimate hazard ratios (HR) and 95% confidence intervals (CI) to determine risk of dying from any cause and risk of developing CRC in higher quintiles of dietary patterns. Test for trend will be performed by modeling the dietary pattern scores as continuous variable and deriving the p-value for trend from the Wald test. In multivariable analyses, we will adjust for: BMI, physical activity, age, energy intake, race/ethnicity, educational status, smoking status, family history of CRC, NSAIDs use and additionally for menopausal status and postmenopausal hormone use in women. We will assess effect modification by BMI and physical activity, and incorporate 2-6 year time lags to reduce the potential for reverse causation. Based on the magnitude of risk explained, we will select the best diet in each of the three approaches (*a priori*, *a posteriori* and hypothesis-driven) and conduct a comparative analysis to derive the overall best diet for a healthful lifestyle that maximizes CRC prevention.

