Aim 1b will be investigated using dietary and biomarker data from the two cohorts in a cross-sectional study. The 8 dietary patterns will be the main exposures while CRC diagnosis will be the outcome of interest. We will calculate dietary patterns from the 2 FFQs closest to the period of blood draw. That is, the 1986 and 1990

FFQs for the NHS, and the 1990 and 1994 FFQs for HPFS, averaging data across the 2 FFQs. We will then conduct mediation analyses, with the main objective of identifying the direct and indirect effects of each dietary pattern on CRC development, i.e., the effect of the dietary pattern that acts through the proposed mediators (CRP, TNF α R2, IL6, adiponectin, C-peptide) (indirect effect) and the effects that are unexplained by these same mediators (direct effects). The traditional approach to mediation analysis is based on adjusting for the mediator in standard regression models to estimate the direct effect, however, this approach may lead to flawed conclusions.⁹⁸ We will therefore use the regression-based approach described by VanderWeele and Vansteelandt⁹⁹ to estimate the direct and indirect effects of each potential mediator one at a time and cumulative effect for multiple mediators. This approach consists of fitting one model for the mediator, and another for the outcome. The approach has the advantage of assessing several mediators in the same model which would efficiently assess the potential interrelatedness of these mediators. We will use the SAS macro developed by the same authors⁹⁹ to implement the mediation analysis. All statistical tests will be two sided, and we will consider 95% confidence intervals not including one as statistically significant.

Expected outcomes for Aim 1 and impact on the field: To our knowledge, an evaluation of the consistency of evidence for the benefits of diet quality for overall health and for CRC prevention, based on a standardized methodology and plausible biological mechanisms has not previously been conducted. With the completion of this study, we anticipate an increased ability to widely translate findings from dietary patterns research and to design guidelines for healthful lifestyles that are optimized for CRC prevention.

C2. Aim 2 – R00 phase: To identify the set of metabolites predicted by both inflammatory diets and by circulating inflammatory markers and then evaluate the association of this unique inflammatory metabolome with CRC risk.

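### Aim 1b averages in an FFQ that follows some blood draws, and may follow an early CRC diagnosis, without a timing rule like that of Aim 1a (minor)

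*Combined protocol and SAP*

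**What the plan says.** The Aim 1b paragraph of C1, Statistical Analysis, sets the exposure by fixed calendar years. It picks the two FFQs nearest the blood draw: the 1986 and 1990 "FFQs for the NHS, and the 1990 and 1994 FFQs for HPFS, averaging data across the 2 FFQs". It labels the design cross-sectional, takes CRC diagnosis as the outcome and the plasma markers as mediators, and aims at direct and indirect effects. It gives no baseline date, no lag and no rule that an FFQ must precede the draw or the diagnosis.

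Other sections of C1 supply the dates:
- Study Population: blood was collected from the NHS ("n=32,826) in 1989-1990 and HPFS (n=18,225) from 1993 to 1994").
- Assessment of biomarkers: "Participants who provided blood samples were cancer free", and the markers come from matched sets ("In the nested case-control studies in which these biomarkers were measured").
- Assessment of dietary data: each FFQ covers the preceding year, and averaging is meant "to reduce within-subject variation and best represent long-term diet".

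Two other analyses do have a timing rule. Aim 1a uses "all available FFQs up to the 2-year interval prior to the follow-up cycle in which death or CRC diagnosis was confirmed" and adds lags of 2-6 years against reverse causation. The case-control analysis of Aims 2 and 3 sets baseline at blood donation.

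**The concern.** Direct and indirect effects are read in the order diet, biomarker, diagnosis. Being cancer free at the draw places diagnosis after the draw, but not after the later FFQ. If the Aim 1b rule is applied as written, an early case's exposure can include diet reported after the CRC diagnosis, and many donors' exposure includes diet reported after blood was drawn. If a diagnosis, or a health state already reflected in the blood, changes diet or its reporting, part of the exposure becomes a consequence of the outcome or of the mediator. The plan guards against the first of these in Aim 1a but does not carry the safeguard into the analysis that relies most on time order.

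**Working it through.** The plan gives no figure to reproduce here. The check is one of date order, followed by illustrations on stated assumptions.

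**1. Date order.** Inputs: draw years from Study Population, FFQ years from Aim 1b. Assume each FFQ is returned within its named calendar year. Then FFQ minus draw lies between (FFQ year − draw year − 1) and (FFQ year − draw year + 1).

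| Draw year | Earlier FFQ (NHS 1986, HPFS 1990) | Later FFQ (NHS 1990, HPFS 1994) |
|---|---|---|
| NHS 1989 or HPFS 1993 | −4 to −2 years: before | 0 to +2 years: after |
| NHS 1990 or HPFS 1994 | −5 to −3 years: before | −1 to +1 year: undetermined |

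The earlier FFQ precedes every draw. A diagnosis between the draw and the later FFQ is possible, in a window of up to two years.

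**2. How much of the exposure lies after the draw.** Assume the draw time D is uniform on (0, 2) years and the later FFQ is returned at time R: at the start of the second year (R = 1), evenly through it, or at its end (R = 2).

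| | R = 1 | R even on (1, 2) | R = 2 |
|---|---|---|---|
| Later FFQ follows the draw, P(R > D) | 50% | 75% | 100% |
| Mean gap, E[max(R − D, 0)], years | 0.25 | 0.583 | 1.00 |
| Later FFQ's recall year after the draw, E[clip(R − D, 0, 1)] | 25% | 50% | 75% |
| Same, halved for the two-FFQ average | 12.5% | 25% | 37.5% |

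**3. Cases diagnosed before the later FFQ.** With even accrual, share = mean gap ÷ follow-up from the mean draw (1990.0 NHS, 1994.0 HPFS).
- To June 2012 (22.4 and 18.4 years): NHS 0.25/22.4 = 1.1% to 1.00/22.4 = 4.5%; HPFS 0.25/18.4 = 1.4% to 1.00/18.4 = 5.4%.
- Table 3 pools the cohorts. At an assumed equal split the share is 1.2-5.0%: about 8-33 of the 666 C-peptide cases, or 15-58 of the 1,179 adiponectin cases.
- The plan gives 2012 for the death and CRC counts, not for the biomarker sets. If the sets closed in mid-2006: NHS 1.5-6.1%, HPFS 2.0-8.1%. If in mid-2000: NHS 2.4-9.6%, HPFS 3.9-15.6%.
- If incidence grows 5% a year to 2012, the share is (e^{0.05g} − 1)/(e^{0.05L} − 1) for gap g and follow-up L: NHS 0.6-2.5%, HPFS 0.8-3.4%.
- With 10-90% of draws in the first year, dates uniform within each year and even accrual over 8-22 years, the later FFQ follows the draw for 55-95% of donors and about 1-11% of cases are diagnosed before it.

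**4. Precision cost of excluding those sets.** The standard error factor is 1/√(1 − p): 1.006 at p = 0.011, 1.028 at 0.054, 1.043 at 0.081, and 1.0885 at 0.156.

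**5. What is lost by using only pre-draw FFQs.** Assume that the biomarker depends on diet at the draw, that true diet has four-year stability s, that FFQ reliability is ρ = 0.6 (e = 1/ρ − 1), and that FFQs fall 0, 4 and 8 years before the draw. The planned average has diet-biomarker correlation proportional to ((1 + s)/2)/√((1 + s + e)/2). The earlier FFQ alone has s√ρ, and two pre-draw FFQs have s times the planned value. For s = 1.0, 0.9 and 0.8 the ratio to planned is 0.894, 0.831 and 0.765 with one FFQ (NHS), and 1.00, 0.90 and 0.80 with two (HPFS).

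**The case against.** The strongest reply is that the choice is deliberate and the harm slight. The FFQs nearest the draw were chosen on purpose, averaging reduces error, and EDII was itself built "from the 1986 and 1990 FFQs in the NHS". A form completed after the draw still describes the preceding year, so much of its recall covers the draw window. This stands. It is why the share is 12.5-37.5% of the averaged recall period and not the half that a reader might infer from the form dates.

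A reader might also infer that the biomarker was measured before the later FFQ, or that participants changed their diet on learning a result. The documents do not support this. They show when blood was drawn. Assays were done in nested case-control sets, with each case and its controls in one batch, which implies assay after the case was identified. For the large majority of cases that is also after the later FFQ.

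Nor do the documents show that the mediation estimates are invalid. As an illustration, suppose diagnosis shifts the later FFQ score by 0.5 SD (assumed). Averaging halves this to 0.25 SD. With 1.2-5.0% of cases affected, the case mean moves by 0.003-0.012 SD. The unmatched standard error of a case-control mean difference is √(1/666 + 1/881) = 0.051 SD for C-peptide and √(1/1,179 + 1/1,643) = 0.038 SD for adiponectin. The shift is therefore about 0.06-0.3 standard errors.

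Finally, the Aim 1a lags could be read as covering all of Aim 1. But they stand in the Aim 1a paragraph, and Aim 1b sets its own fixed FFQ years without repeating them. A lag before diagnosis would also not put the FFQ before the draw.

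**Conclusion.** The point holds as a minor, inexpensive improvement. It is certain from the documents that the later FFQ follows every 1989 or 1993 draw and that Aim 1b states no timing rule. It is possible, but cannot be counted, that the later FFQ also follows the diagnosis of some early cases: about 1-5% under even accrual to 2012, and 0.6-15.6% across all assumptions tried. The top figure needs HPFS sets closing in mid-2000 and the latest FFQ return. The order for 1990 and 1994 draws cannot be determined. Bias is nil if neither diagnosis nor an underlying health state alters later diet or its reporting; otherwise it is probably small. The cross-sectional label is a wording matter and adds no weight to the timing point.

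**What to change.** 1. Keep the two-FFQ average as the main Aim 1b exposure, but exclude cases diagnosed before their later FFQ was returned, together with their matched controls. Do not substitute a single FFQ for those sets, because that mixes exposures of different reliability.
2. Prespecify a sensitivity analysis of the direct and indirect effects using only FFQs from before the draw window: 1986 for NHS, 1986 and 1990 for HPFS. NHS has one because the plan says "Dietary data are updated every four years in the NHS (since 1980", and a four-year step from 1980 does not reach 1986, so no earlier NHS year can be named from the documents. Report it by cohort and read it only as a check on FFQ timing, since it cannot separate feedback from attenuation.
3. As wording only, describe Aim 1b as a nested case-control analysis with prospectively collected blood.

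Cost: SAP wording and one extra model run on FFQs already on file. For item 1, standard errors widen by about 0.6-2.8% if 1.1-5.4% of case sets are dropped, 4.3% at 8.1%, and just under 9% at 15.6%. For item 2, under the assumptions in the working, the diet-biomarker correlation falls by 11-24% in NHS and 0-20% in HPFS, which is why it should not be the main analysis.

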Expected outcomes for aims 2 and 3 and impact on the field: We anticipate identifying key metabolic pathways in CRC based on unique metabolomes that are the joint effect of dietary preferences and circulating biomarkers. In addition, we expect to find metabolites of uncertain, and possible pathogenic significance related to CRC risk. Therefore we will uncover potentially actionable metabolomes and

specific metabolites for prevention and early detection. Findings from these aims will identify the biological mechanisms by which dietary patterns relate to CRC risk, and along with our findings from Aim 1, we will develop a more comprehensive understanding of how to improve the efficiency of dietary recommendations optimized for CRC prevention.

Sample size and statistical power considerations (all Aims): Table 3 illustrates case counts up to 2012 for all-cause death and CRC in NHS and HPFS, including the magnitude of association that can be achieved with 80% power given the sample sizes for the various hypotheses.¹⁰⁴⁻¹⁰⁶ We will thus have ample power to detect significant associations. We also anticipate large precision (narrow 95% CIs) in these analyses.

Limitations and alternative strategies (all Aims): *Bias due to incomplete follow-up is possible.* Thus we devote great effort to follow-up, with 93% cumulative follow-up. Differential CRC screening intensity could create bias, but we do not expect endoscopy rates to vary appreciably by exposure status. *Misclassification of exposures* is

always present to some degree. We have documented extensively the validity of our dietary questionnaire, which is further enhanced by repeated administrations. The data from our validation/calibration studies and studies of within-person variation of biomarkers allow us to adjust RRs and CIs for measurement error using methods we have developed.¹⁰⁷⁻¹¹⁰ We also conducted extensive pilot studies to assess

metabolites based on our *a priori* QC criteria, and excluded metabolites that did not pass these criteria.¹⁰² *Confounding* due to unmeasured or imperfectly measured covariates can be present. Thus, we strive to assess any plausible confounding variables and will conduct extensive multivariable-adjusted analyses.

Representativeness of a single blood sample to reflect long-term levels is a potential concern. However, our data above indicate that the ICCs over 2-3 years for most proposed metabolites are 0.48-0.72.

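### Aim 1b splits diet effects on CRC using markers from one blood collection, with no correction for within-person error, so the mediated share is expected to be too low

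*Combined protocol and SAP*

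**What the plan says.** All places are in the combined protocol and SAP.

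- **C1, Statistical Analysis, Aim 1b.** The indirect effect is the part of a dietary pattern's effect that acts through the five markers. The direct effect is "the effects that are unexplained by these same mediators (direct effects". On method: "This approach consists of fitting one model for the mediator, and another for the outcome". The aim is to "estimate the direct and indirect effects of each potential mediator one at a time and cumulative effect for multiple mediators", using a published SAS macro. Diet is averaged over two questionnaires. No averaging of markers and no error correction is described.
- **C1, Study Population.** "Blood samples were collected from subpopulations of the NHS (n=32,826) in 1989-1990 and HPFS (n=18,225) from 1993 to 1994".
- **C1, Assessment of biomarkers.** For the markers, only intra-assay coefficients of variation are given (for example 2.9% to 12.8% for IL6). These measure laboratory error, not variation within a person over time.
- **Limitations and alternative strategies (all Aims).** The plan recognises the issue: "Representativeness of a single blood sample to reflect long-term levels is a potential concern". Its reply is that "the ICCs over 2-3 years for most proposed metabolites are 0.48-0.72", which concerns metabolites. Under misclassification of exposures it adds that "studies of within-person variation of biomarkers allow us to adjust RRs and CIs for measurement error using methods we have developed".

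**The concern.** Aim 1b asks whether diet affects CRC through inflammation and insulin. Long-term marker level is the quantity of interest, and a single draw measures it with error. Random error in a mediator leaves the diet-to-marker slope unbiased but shrinks the marker-to-CRC slope. The product of the two, the indirect effect, shrinks with it. The direct effect is the remainder, so it takes up what is lost.

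A small indirect effect could then mean that the marker mediates little, or that it was measured with much error. The planned output cannot tell these apart. Two markers that mediate equally could also look different only because one is more stable within a person. The plan rejects the traditional mediation approach because it can mislead, so a valid split is its own goal.

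**Working it through.** **Figures to reproduce.** There are none. The documents state no direct or indirect effect, no proportion mediated and no reliability for the five markers. The 1b rows of Table 3 give detectable diet–marker and marker–CRC associations only.

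**Assumptions (not in the documents).** Diet and true marker have unit variance; diet–marker correlation r = 0.25; no diet–marker interaction; classical non-differential error; marker reliability ρ from 0.4 to 0.8; true mediated share 50%.

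**1. Marker error only.** With diet in the model, the marker slope is multiplied by

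λ = ρ(1 − r²) / (1 − ρr²), with r² = 0.0625.

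The total effect is unchanged, so the observed share is 0.50 × λ.

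| ρ | λ | Observed share |
|---|---|---|
| 0.8 | 0.750/0.950 = 0.789 | 39% |
| 0.6 | 0.5625/0.9625 = 0.584 | 29% |
| 0.5 | 0.46875/0.96875 = 0.484 | 24% |
| 0.4 | 0.375/0.975 = 0.385 | 19% |

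Varying r from 0.1 to 0.3 changes little: at ρ = 0.6 the share is 30% and 29%.

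*Simulation check.* A logistic simulation with 1.5 million subjects gave a share of 49% without error, 35% at ρ = 0.72 and 25% at ρ = 0.48. The formula gives 35% and 23% for the last two. The direct log-odds ratio rose from 0.051 to 0.065 and 0.076, while the total stayed near 0.101.

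**2. Adding diet error.** Assume questionnaire reliability k = 0.6. Set the true marker slope to 1 and the true direct effect to 0.25, so the true indirect effect is 0.25 × 1 = 0.25. Then:

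- Observed diet variance is 1/0.6 = 1.667, and observed marker variance is 1/ρ.
- Covariances with the outcome are 0.25 + 0.25 = 0.50 (diet) and 0.25 × 0.25 + 1 = 1.0625 (marker).
- Marker slope = (1.667 × 1.0625 − 0.25 × 0.50)/D = 1.646/D, where D = 1.667/ρ − 0.0625.
- Diet-to-marker slope = 0.25 × 0.6 = 0.15. Total effect = 0.6 × 0.50 = 0.30.

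| ρ | D | Indirect = 0.15 × 1.646/D | Share of 0.30 | Direct ÷ true 0.25 |
|---|---|---|---|---|
| 0.8 | 2.021 | 0.122 | 41% | 0.71 |
| 0.6 | 2.715 | 0.091 | 30% | 0.84 |
| 0.5 | 3.271 | 0.075 | 25% | 0.90 |
| 0.4 | 4.104 | 0.060 | 20% | 0.96 |

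The share is still too low, but the direct effect is now below its true value as well.

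**3. Two markers.** Analysed one at a time, markers with equal true indirect effects but reliabilities 0.8 and 0.5 would differ by 0.789/0.484 = 1.6-fold.

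For the joint model, assume marker correlation 0.4, independent errors, and true slopes of 0.1 each (indirect effects 0.25 × 0.1 = 0.025). Given diet:

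- True marker variance is 0.9375 and covariance 0.4 − 0.0625 = 0.3375.
- Observed variances are 0.9375 + 0.25 = 1.1875 and 0.9375 + 1 = 1.9375.
- Determinant = 1.1875 × 1.9375 − 0.3375² = 2.187. The right-hand side is (0.9375 + 0.3375) × 0.1 = 0.1275 for each marker.
- Slopes: 0.1275 × (1.9375 − 0.3375)/2.187 = 0.0933 and 0.1275 × (1.1875 − 0.3375)/2.187 = 0.0496.
- Indirect effects: 0.25 times these, 0.023 and 0.012, a ratio of about 1.9.

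If the errors are themselves correlated, a single marker's share in a joint model can move either way.

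**4. Laboratory error alone.** At the largest quoted CV (12.8%) and an assumed between-person log SD of 0.3 to 0.8, reliability is s²/(s² + 0.128²) = 0.85 to 0.98. The concern therefore rests on variation over time, which the assay CVs do not address.

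**The case against.** The strongest reply is that the plan does deal with measurement error. The limitations section covers all Aims, names within-person biomarker data, recognises the single sample, and cites correction methods, including one titled for several covariates measured with error. This stands in part: a reader who infers that the plan ignores marker error would be wrong. But the sentence states what the data allow, not what will be done. Aim 1b does not take it up, and the single-sample reply quotes metabolites.

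Other stronger readings also fail:

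- *The direct effect is inflated in size.* This holds with marker error alone. With diet error added, the direct effect can be too small (step 2). It is the mediated share that is too low in both cases.
- *The plan favours the most stable marker.* It states no ranking or comparison rule. The risk lies in how results are read side by side.
- *Correcting relative risks cannot repair the split.* It can, if the corrected marker coefficient is carried into the direct and indirect effects. The plan does not say that it will be.
- *A finding of mainly direct effects would be an artefact.* Not necessarily. With a true share of 20%, 20% × λ is 16%, 12% and 8% at reliability 0.8, 0.6 and 0.4, and the effect really is mainly direct.
- *The one sample stands for marker levels up to 2012.* That date is given for Aim 1a and for the Table 3 case counts; the Aim 1b text states no end of follow-up.

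It is also fair to say that defining the direct effect relative to named mediators is not in itself an error.

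**Conclusion.** The concern holds for the mediated share. Run as written, Aim 1b is expected to understate the share carried by each marker in the one-at-a-time analyses. This rests on classical, non-differential error, direct and indirect effects of the same sign, and no diet–marker interaction. On the assumed inputs, a true 50% would appear as roughly 19% to 39%, or 20% to 41% with diet error added. Those figures are illustrations: reliability, correlation and true share are all assumed, and the documents do not allow the actual bias to be computed. Differences between markers may partly reflect differing reliability, but for joint models the documents support no general statement on direction. The gap is a correction that the plan says is possible but does not prespecify for this analysis. It should be closed before Aim 1b is interpreted; it does not invalidate the two-model approach.

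**What to change.** Keep the planned mediation analysis and add the following to Aim 1b:

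1. State the within-person reliability of each of the five markers, with its source.
2. Apply the correction methods cited in the limitations section to the marker coefficients in the outcome model, with reliability taken conditional on diet and covariates. Use the multiple-covariate version for joint models.
3. Recompute direct and indirect effects from the corrected coefficients, with intervals that include the uncertainty in reliability (for example by bootstrap). Report them beside the uncorrected estimates.
4. For a marker without reliability data, show results over an assumed range such as 0.4–0.8.
5. Do not conclude that an effect is mainly direct, or that one marker mediates more than another, unless this holds in the corrected results. Describe the remainder as not explained by the measured markers.

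Correcting marker error alone leaves attenuation from diet error. In step 2 of the check with ρ = 1, D = 1.604, the indirect effect is 0.15 × 1.646/1.604 = 0.154 and the share is 0.154/0.30 = 51%. The direct effect is 0.146/0.25 = 0.58 of its true value. The report should say so.

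The cost is extra analysis with data and methods the plan says are held, and no new assays. The downside is wider intervals for the corrected indirect effects.
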